5.6 Total Number of Participants and Sites

Recruitment will end when approximately 60 participants are enrolled at this single site at NYUMC. It is expected that approximately 60 participants will need to be enrolled in order to retain 40 evaluable participants at 12 weeks of follow up (an overall 33% drop out rate).

CONFIDENTIAL

This material is the property of the NYU School of Medicine and Langone Medical Center. Do not disclose or use except as authorized in writing by the study sponsor
Interventional Template Version: 11 January 2019

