7.2.5 Withdrawal/Early Termination Visit

If 12 weeks of study agent usage:

- Record AE as reported by participant or observed by investigator
- Record participant's adherence to treatment regimen
- Obtain GSM symptom history, and record VAS scores for dyspareunia, itching, and dryness
- Record vital signs, results of physical exam including pelvic
- Collect pelvic samples for vaginal pH and vaginal tissue scraping for vaginal maturation index
- Have patient fill out VSQ
- Discuss the obvious, preliminary changes in their symptoms, if any exist
- Provide contact information for [name] to communicate any AE or side-effect experienced after the end of the study if patient believes it is related to the study

If <12 weeks of study agent usage:

- Record AE as reported by participant or observed by investigator
- Record participant's adherence to treatment regimen
- Record vital signs, results of physical exam including pelvic
- Provide contact information for [name] to communicate any AE or side-effect experienced after the end of the study if patient believes it is related to the study

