10.4 Description of Statistical Methods

Baseline (pre-randomization) participant demographics and clinical characteristics will be summarized through descriptive statistics overall, and by randomized group. Clinical characteristics will include past HRT use, uterus present or not, and components of their medical and gynecologic history. Details of each outcome measure is provided below. Analysis of the primary and secondary measures will include summarizing each by the mean and standard deviation at baseline and all measured time points, including at the primary outcome time of 12 weeks. For continuous measures, a linear mixed effects regression model will estimate the mean outcome at 12 weeks, both unadjusted and adjusted for baseline measurement. No further adjustment for participant characteristics is expected given the limited trial size. The linear mixed effects regression model will allow all participants to be included in analysis, regardless of completion of study follow up at 12 weeks, under the assumption of this assessment being missing at random.

Missing outcome data will be summarized by participant characteristics to understand how to better retain individuals in treatment.

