10.4.5.1 Safety Review

There are no anticipated side-effects to the investigational agent. The control agent is FDA approved for the condition being studied in this trial. Thus, study enrollment will only be stopped if unforeseeable, significant side effects or life-threatening adverse events occur in either study cohort. No statistical rules will be used to halt enrollment due to the short duration of the study and lack of interim analysis.

Patients will be counseled at the start of the study to call [name] or [name] for any side-effect or AE they believe is related to study medication usage. Otherwise, after the baseline visit, the next formal visit will be the final visit at week 12 when medication safety questions will be asked.

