10.5 Sample Size

This study would be the first US-based randomized trial investigating HLA's usage for GSM treatment, to the authors' best knowledge. Thus, the sample size of 60 has been chosen to pilot the presented protocol, to assess feasibility and acceptability in quality of life for HLAs and to gather preliminary effectiveness for planning a larger effectiveness trial. The authors acknowledge the limitations of having enrolling 60 individuals, including generalizability. However in this initial stage of study implementation and design, expect this number to provide sufficient information.

No study to date has used the VSQ to assess the impact of treatment modalities for GSM, so there is no historical data to provide an assumed mean score. However, with 30 individuals randomized to each study treatment, we expect to have at least 80% probability of achieving a 95% confidence interval (CI) width of 1.7, assuming a standard deviation in the VLM of 2. With fewer individuals at any timepoint, the width of the CI will increase.

The assumed drop-out, withdrawal, cross-over and missing data rate is assumed to be 33%, which explains the enrollment goal of 60 to allow for 40 evaluable patients. This is a conservative estimate because the missing data rates in RCT's from four major journals has shown to be 20% or greater in about 18% of trials, which was also seen in quality-of-life studies (26, 27). We will monitor reasons for drop out and withdrawal of treatment to improve study adherence and follow up.

All participants will be included in the intent to treat analyses, and those participants who use the study intervention for at least 12 weeks will be included in the per-protocol analysis.

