10.6 Measures to Minimize Bias

10.6.1 Enrollment/Randomization/Masking Procedures

While blinding would be desired in this study, it is not feasible due to the study drugs having different formulations. Therefore, once randomization is performed, investigators and patients will know which study arm patients are assigned to. The implication of lack of blinding is that there could be potential bias regarding patient report of symptomatic improvement and provider record of measurements, such as VAS scores. However, the goal of this study is to be a pilot study to allow for a larger RCT in the future that could potentially be blinded and allow for minimization of biases.

To reduce bias, randomization will be used with allocation 1:1 to each treatment group. Block randomization will be used due to the small sample size of each study arm using Trialmaster. Replacement of patients who discontinue will not be allowed since the enrollment goal of 60 is conservative to account for drop-outs, early discontinuation, and lost to follow up patients.

11 Source Documents and Access to Source Data/Documents

Source data is all information, original records of clinical findings, observations, or other activities in a clinical trial necessary for the reconstruction and evaluation of the trial. Source data are contained in source documents. Examples of these original documents, and data records include: hospital records, clinical and office charts, laboratory notes, memoranda, subjects'

CONFIDENTIAL

This material is the property of the NYU School of Medicine and Langone Medical Center. Do not disclose or use except as authorized in writing by the study sponsor
Interventional Template Version: 11 January 2019

diaries or evaluation checklists, pharmacy dispensing records, recorded data from automated instruments, copies or transcriptions certified after verification as being accurate and complete, microfiches, photographic negatives, microfilm or magnetic media, x-rays, subject files, and records kept at the pharmacy, at the laboratories, and at medico-technical departments involved in the clinical trial. It is acceptable to use CRFs as source documents. If this is the case, it should be stated in this section what data will be collected on CRFs and what data will be collected from other sources.

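### Up to 33% loss is planned, but the primary VSQ analysis rests on a doubtful and untested missing-at-random assumption, and the sections do not settle whether the VSQ is collected after early stopping

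*Combined protocol and SAP*

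**What the plan says.** - **Analysis.** Section 10.4 uses a linear mixed model for continuous outcomes, unadjusted and adjusted for baseline, with no other covariate expected. It includes women "regardless of completion of study follow up at 12 weeks, under the assumption of this assessment being missing at random". The only other step for missing outcomes is a descriptive summary by participant characteristics, meant to improve retention. Sections 10.3 and 10.5 add a per-protocol set of women with at least 12 weeks of use.
- **Visits.** Section 10.4.5.1: "after the baseline visit, the next formal visit will be the final visit at week 12".
- **Loss.** Section 10.5: "The assumed drop-out, withdrawal, cross-over and missing data rate is assumed to be 33" percent. Section 5.6 treats the same figure as drop-out, enrolling about 60 to "retain 40 evaluable participants at 12 weeks of follow up (an overall 33% drop out rate".
- **VSQ collection.** Section 7.2.5 has two lists. The one headed "If <12 weeks of study agent usage" covers adverse events, adherence, vital signs, examination and contact details, but not the VSQ, which appears only in the list for 12 weeks of use. Section 5.7.2 arranges a week-12 office visit for women who withdraw or are terminated, whatever their participation. It does not name the VSQ, and its fallback phone call covers safety only. Section 7.2.4 and the Schedule of Events list the VSQ at Visit 2 with no condition on use.
- **Adherence.** Sections 2.1 and 4.2.1 say that women who feel their symptoms improve are likely to keep to treatment.

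**The concern.** A woman without a week-12 VSQ contributes only her baseline score. The model in effect gives her the week-12 value of completers in her arm with the same baseline. That is right only if, given arm and baseline, whether her score is missing is unrelated to what it would have been.

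The protocol gives a reason to doubt this. It expects continued use to follow perceived improvement, and one of its sections makes VSQ collection depend on continued use. If women who gain little stop early and are not asked, the arm means look too favourable. The trial is open label. Section 6.1.8 foresees stopping for side effects on estrogen, while 10.4.5.1 anticipates none on hyaluronic acid (HLA). Reasons for stopping may therefore differ by arm, and the bias need not cancel in the difference. Section 10.2 intends these estimates for planning later trials, so any optimism would carry forward.

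**Working it through.** **Inputs from the documents**
- 30 women per arm: "with 30 individuals randomized to each study treatment" (10.5), with 1:1 allocation, "randomization will be used with allocation 1:1 to each treatment group" (10.6.1).
- 33% loss, leaving 40 evaluable, or 20 per arm if loss is equal.
- SD 2: "assuming a standard deviation in the VLM of 2" (10.5). VLM is not defined; taking it to be the VSQ is an assumption.

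**Further assumptions**
- Delta is the average amount by which missing women's true week-12 VSQ is worse (higher) than the model predicts. I use 1, 2 and 3 points. Section 10.5 says no treatment study has used the VSQ, so the documents supply no value.
- The missing fraction f is 1/3 if the whole allowance is missing VSQ. I also use 20%, because the allowance includes cross-overs, who may have a VSQ.

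**1. The plan's own figures.** 40/(1 − 0.33) = 59.7, rounded to 60, as stated. For one arm's mean with n = 30 and SD 2, the expected 95% CI width is 2 × 2.045 × 2/√30 = 1.49, and the probability that the width is at most 1.7 is 0.87. The claim of at least 80% holds for a single arm's mean. At n = 20 the expected width is 2 × 2.093 × 2/√20 = 1.87.

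**2. What the assumption can condition on.** Section 10.1 promises treatment effects, so arm must be in the model. Baseline VSQ enters the adjusted version. There is no intermediate VSQ and no other covariate, so the conditioning set is arm and baseline at most.

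**3. Whether any planned analysis departs from the assumption.** The unadjusted and adjusted models share it. The per-protocol set selects on 12 weeks of use, so it cannot probe what happened to women who stopped. The summary of missingness describes who is missing, not how the estimate depends on them.

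**4. Shift in an arm mean = f × delta**

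| Delta (assumed) | f = 1/3 | f = 0.20 |
|---|---|---|
| 1 | 0.33 | 0.2 |
| 2 | 0.67 | 0.4 |
| 3 | 1.00 | 0.6 |

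**5. Shift in the between-arm difference.** If the gap occurs in one arm only, the whole amount in step 4 enters the difference. If delta is equal in both arms, the shift is (f₁ − f₂) × delta. This is 0 with equal loss. With 14 of 30 missing in one arm and 6 of 30 in the other (still 20 of 60), it is 0.267 × 2 = 0.53 for delta 2.

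**6. Yardsticks.** The 95% CI half-width for the difference at 20 per arm is 2.024 × 2 × √(2/20) = 1.28. The planned half-width for one arm's mean is 1.7/2 = 0.85. With f = 1/3, a delta of 0.85/(1/3) = 2.55 would move the arm mean by that much.

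**7. Whether such deltas can arise.** In an illustrative simulation (SD 2, assumed baseline correlation 0.5, one third missing), the log-odds of being missing rose by 0.5 or 1.0 per point of the unobserved week-12 score. Missing women were on average 1.31 or 2.01 points worse than predicted. The baseline-adjusted mean was too favourable by 1.31 × 0.333 = 0.44 or 2.01 × 0.334 = 0.67. This shows only that the mechanism can produce gaps within the assumed range.

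**The case against.** **The procedure does not contradict the assumption.** A reader might infer that the plan's own rules refute missing at random, because stopping treatment causes the VSQ to be missing. The documents do not support that. Missing at random fails only if, given arm and baseline, missingness depends on the unseen score. Stopping because of travel, or a side effect unrelated to vulvovaginal symptoms, need not violate it. Unequal loss between arms is not enough by itself either, because the model conditions on arm.

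**Stopping the product need not mean a missing VSQ.** Sections 6.1.8 and 7.2.6 separate stopping the agent from leaving the study. A woman who stops but attends Visit 2 has a VSQ listed under 7.2.4, and 5.7.2 arranges a week-12 visit even for those who withdraw. This stands in part: the sections can be read either way. But 5.7.2 names no VSQ, 7.2.5 leaves it out, and women who refuse the visit or are lost would still be missing.

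**The 33% is not a forecast of missing VSQ.** It pools several causes and section 10.5 calls it conservative. This stands, so the shifts scale down with the fraction actually missing.

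**It is a pilot.** Section 10.1 puts formal comparison outside the focus, and 10.4.4 tabulates discontinuation reasons where given. This lowers the stakes, and it means a tipping point has no test or margin to tip. It does not remove the use of the estimates for planning.

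**Conclusion.** The point holds in a limited form. Missing at random given arm and baseline is the only basis for handling missing VSQ scores. The protocol's own expectation about adherence makes it doubtful, and nothing planned tests it. Sections 5.7.2, 7.2.4 and 7.2.5 leave open whether women who stop early are asked for the VSQ.

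The possible optimism in an arm mean runs from 0.2 point (20% missing, delta 1) to 1.0 point (one third missing, delta 3). Even the largest one-arm shift in this range stays below the 1.28 half-width of the difference, so it would not by itself overwhelm the interval. At one third missing, though, a delta of 3 exceeds the 0.85 planned for a single arm's mean. These sizes rest on assumed deltas, on reading VLM as the VSQ, and on the fraction actually missing. They show sensitivity and do not predict bias. This is a worthwhile, inexpensive improvement, not a flaw that invalidates the pilot.

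**What to change.** 1. Reconcile 5.7.2, 7.2.4 and 7.2.5, and state that the VSQ is collected at the week-12 visit already arranged, whether or not the woman was still using the product. This reduces the missing data directly.
2. Add to 10.4 a delta-adjusted sensitivity analysis of the week-12 VSQ. Impute the values still missing under the primary model, then worsen them by 0, 1, 2 and 3 points, varied separately by arm. Report how each arm mean, the between-arm difference and their 95% CIs move. Do not define a significance-based tipping point, because the plan has no test or margin.

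The cost is a short SAP paragraph, one questionnaire at a visit already arranged, and a little more analysis work.

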10.4.1 Analysis of the Primary Endpoint

- VSQ score (see attached below):
 - Definition: 21 question survey
 - Interval variable overall (binary responses; a 'yes' equates to one point, a 'no' equates to zero points for each question which is then added up to a sum)
 - Single endpoint measure with a score that can range from 0 to 21

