4.2 Study Endpoints

4.2.1 Primary Study Endpoints

The primary endpoint will be the change in the VSQ score, between the baseline visit and 12 week follow-up.

The VSQ is a 21-question survey developed in 2012 that specifically asks about GSM symptoms, their emotional impact, sexual impact, and life impact. Among 120 post-menopausal women, this questionnaire was found to have reliability and internal consistency (15). Most importantly, in the absence of a gold standard instrument to assess the quality of life impact of

CONFIDENTIAL

This material is the property of the NYU School of Medicine and Langone Medical Center. Do not disclose or use except as authorized in writing by the study sponsor
Interventional Template Version: 11 January 2019

GSM, this questionnaire is critical. It is more nuanced and disease-specific than VAS scoring, and thus far, an underutilized tool to understand the significant psychological impact of this disease. Because GSM is a symptom-driven disease and patients will likely adhere to a treatment plan if they perceive symptomatic improvement, this study's primary endpoint of treatment success will be measured by improvement in VSQ scoring.

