The study case report form (CRF) is the primary data collection instrument for the study. All data requested on the CRF must be recorded. All missing data must be explained. If a space on the CRF is left blank because the procedure was not done or the question was not asked, write "N/D". If the item is not applicable to the individual case, write "N/A". All entries should be printed legibly in black ink. If any entry error has been made, to correct such an error, draw a single straight line through the incorrect entry and enter the correct data above it. All such changes must be initialed and dated. DO NOT ERASE OR WHITE OUT ERRORS. For clarification of illegible or uncertain entries, print the clarification above the item, then initial and date it.

Access to study records will be limited to IRB-approved members of the study team. The investigator will permit study-related monitoring, audits, and inspections by the IRB/EC, the sponsor, government regulatory bodies, and University compliance and quality assurance groups of all study related documents (e.g. source documents, regulatory documents, data collection instruments, study data etc.). The investigator will ensure the capability for inspections of applicable study-related facilities (e.g. pharmacy, diagnostic laboratory, etc.).

Participation as an investigator in this study implies acceptance of potential inspection by government regulatory authorities and applicable University compliance and quality assurance offices.

12 Quality Assurance and Quality Control

QC procedures will be implemented beginning with the data entry system and data QC checks that will be run on the database will be generated. Any missing data or data anomalies will be communicated to the site(s) for clarification/resolution.

Following written SOPs, the monitors will verify that the clinical trial is conducted and data are generated, documented (recorded), and reported in compliance with the protocol, GCP, and the applicable regulatory requirements (e.g., Good Laboratory Practices (GLP), Good Manufacturing Practices (GMP)).

The investigational site will provide direct access to all trial related sites, source data/documents, and reports for the purpose of monitoring and auditing by the sponsor, and inspection by local and regulatory authorities.

CONFIDENTIAL

This material is the property of the NYU School of Medicine and Langone Medical Center. Do not disclose or use except as authorized in writing by the study sponsor

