27. National Research Council. The prevention and treatment of missing data in clinical trials. National Academies Press, 2010.

CONFIDENTIAL

This material is the property of the NYU School of Medicine and Langone Medical Center. Do not disclose or use except as authorized in writing by the study sponsor
Interventional Template Version: 11 January 2019

19 Attachments

19a The Vulvovaginal Symptom Questionnaire

The Vulvovaginal Symptom Questionnaire

The following questions were developed to assess skin symptoms of women. The skin surrounding the vagina is called the vulva. Just like skin in other parts of the body, the vulva can sometimes become irritated. Many women experience discomfort in the region of the vulva. These symptoms may be mild, but can sometimes be severe. The following questions will ask you about your vulvar skin symptoms during the past week.

During the past week, have you been bothered by:

1. Your vulva itching? No Yes
2. Your vulva burning or stinging? No Yes
3. Your vulva hurting? No Yes
4. Your vulva being irritated? No Yes
5. Your vulva being dry? No Yes
6. Discharge from your vulva or vagina? No Yes
7. Odor from your vulva or vagina? No Yes
8. Worry about your vulvar symptoms?
(for example, that it will spread, get worse, scar, etc.) No Yes
9. The appearance of your vulva? No Yes
10. Frustration about your vulvar symptoms? No Yes
11. Embarrassment about your vulvar symptoms? No Yes
12. The effects of your vulvar symptoms on your interactions with others? No Yes
13. The effects of your vulvar symptoms on your desire to be with people? No Yes
14. Your vulvar symptoms making it hard to show affection? No Yes
15. The effects of your vulvar symptoms on your daily activities? No Yes
16. Your vulvar symptoms affecting your desire to be intimate? No Yes
17. Are you currently sexually active with a partner?
 No → Thank you. You are done with this questionnaire.
 Yes → Please proceed with the next 4 questions
18. The effects of your vulvar symptoms on your sexual relationships? No Yes
19. Your vulvar symptoms causing pain during sexual activity? No Yes
20. Your vulvar symptoms causing dryness during sexual activity? No Yes
21. Your vulvar symptoms causing bleeding during sexual activity? No Yes

CONFIDENTIAL

This material is the property of the NYU School of Medicine and Langone Medical Center. Do not disclose or use except as authorized in writing by the study sponsor
Interventional Template Version: 11 January 2019

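### The primary VSQ sum counts being sexually active (item 17) as a point of worse disease, and the plan does not say how items 18–21 score when they are skipped

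*Combined protocol and SAP*

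**What the plan says.** Section 4.2.1 states: "The primary endpoint will be the change in the VSQ score", measured from baseline to week 12. Section 10.4.1 defines the score over all 21 questions. A yes earns one point and a no "equates to zero points for each question which is then added up to a sum". The result is described as a "Single endpoint measure with a score that can range from 0 to 21".

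In the form at Attachment 19a, one of the 21 questions is "17. Are you currently sexually active with a partner". A no leads to "Thank you. You are done with this questionnaire"; a yes leads to "Please proceed with the next 4 questions".

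Three other places bear on the point:
- Section 11, on completing the CRF, says "If the item is not applicable to the individual case, write" N/A. Section 10.4.1 gives N/A no value.
- Section 10.4 estimates the 12-week mean "both unadjusted and adjusted for baseline measurement" and expects no other adjustment. Its missing-at-random statement concerns an absent 12-week assessment, not items the form tells the woman to skip.
- Section 5.1 does not require sexual activity for entry, so active and inactive women can both enrol.

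No section takes item 17 out of the sum or says how skipped items 18–21 are scored.

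**The concern.** Item 17 is neither a symptom nor an impact. It decides whether four further items are asked. Under the stated rule, a yes to it raises the score by one point, in the direction of worse disease. A woman who resumes sexual activity during the trial is therefore scored as worse for that reason alone, and one who stops as better.

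The silence on items 18–21 adds a second problem. Two analysts following Section 10.4.1 could reach different primary results, one letting skipped items add nothing and the other treating them as missing.

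The trial is a pilot and does not focus on hypothesis testing. But Section 10.1 plans treatment effects with 95% confidence intervals, Section 10.2 passes the estimates to future trials, and Section 10.5 says there are no earlier treatment data on the VSQ. Section 10.6.1 makes the trial open label, so a scoring rule chosen after data are seen would be chosen with allocation known.

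**Working it through.** **Reproducing the stated range (form in Attachment 19a, rule in Section 10.4.1).**
- Items 1–16, asked of everyone: 16.
- Items 18–21, asked only if item 17 is yes: 4.
- Symptom or impact items: 16 + 4 = 20. Item 17 is the 21st question.
- The stated maximum: 16 + 1 + 4 = 21. It reproduces only if a yes to item 17 earns a point.

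**Range by activity status, skipped items adding nothing.**
- Inactive: 0 to 16.
- Active: minimum 1 + 0 = 1; maximum 1 + 16 + 4 = 21.

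**Shift when status changes, items 1–16 held fixed.** Let k (0 to 4) be the number of items 18–21 answered yes at the active visit.
- Starting activity: +(1 + k), so +1 to +5. Stopping: −1 to −5.
- With item 17 removed: k, so 0 to 4 in either direction.
- Same status at both visits: item 17 contributes equally at each visit and cancels from the raw change. It does not cancel from the unadjusted 12-week mean, where any difference between arms in the share of active women also enters.

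**Skipped items treated as missing instead.** A woman has no total at any visit where she is inactive, and so no raw change if that is either visit.

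**Effect of one such woman on her arm's mean change.**

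| Evaluable per arm | As written | Item 17 removed |
|---|---|---|
| 20 | 1/20 to 5/20 = 0.05–0.25 | 0 to 4/20 = 0–0.20 |
| 30 | 1/30 to 5/30 = 0.03–0.17 | 0 to 4/30 = 0–0.13 |

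The 30 is the number randomised per arm in Section 10.5; the 20 is half of the 40 evaluable women expected there.

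**Illustration of between-arm bias.** The documents give no rate of status change, so the rates here are assumptions. Suppose the net rate (starters minus stoppers) differs between arms and the shift has the same size for all switchers. Bias = difference in net rate × (1 + k):
- 5 percentage points: 0.05–0.25
- 10 percentage points: 0.1–0.5
- 20 percentage points: 0.2–1.0

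If the shifts differ in size, equal rates do not guarantee zero bias. With 10% starting and 10% stopping in both arms, stoppers at −3 in both, and starters at +1 in one arm and +5 in the other: (0.1×5 − 0.1×3) − (0.1×1 − 0.1×3) = 0.2 − (−0.2) = 0.4.

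**Scale.** Between-arm 95% half-width = t(0.975, 2n − 2) × SD × √(2/n). With the SD of 2 in Section 10.5:
- n = 30: 2.002 × 2 × 0.258 = 1.03
- n = 20: 2.024 × 2 × 0.316 = 1.28

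Section 10.5 attaches that SD to an undefined abbreviation (VLM); reading it as the SD of VSQ change is an assumption.

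**The case against.** Several points on the other side are fair.

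- **Not all of the 1 to 5 points is artefact.** A reader might infer that the whole shift is spurious. The documents do not support that. A woman who resumes activity and reports pain, dryness or bleeding is reporting real symptoms, and Sections 2.1 and 4.2.1 describe the VSQ as covering sexual impact. Only the item 17 point is plainly spurious, and the full 5 needs all four later items endorsed. Holding items 1–16 fixed is also a simplification, since items 14 and 16 concern affection and desire for intimacy.
- **The shift depends on the reading.** It arises if skipped items add nothing. That is the literal sum, because only a yes earns points, but it is not stated.
- **No bias for or against HLA is shown.** A reader might infer one. Attachment 19b says the insert is meant to ease sexual activity, and Section 2.4.2 reports better sexual function with vaginal estrogen tablets. Neither shows that activity status changes, and either arm could be affected. All the equal-shift illustrations lie below the between-arm half-width.
- **No inflation of the SD is shown.** Assume the SD of 2 is for items 1–16 and 10% start and 10% stop. With one-point shifts independent of items 1–16, the SD becomes √(4 + 0.2) = 2.05. If starters improve one point more and stoppers one point less on items 1–16, it falls to √(4 + 0.2 − 0.4) = 1.95.
- **The damage is recoverable.** Item responses are collected at both visits, so totals can be recomputed. Section 10.2 also says baseline differences will be considered.

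These limit the size of the claim. They do not remove the contradiction between the stated range and the form, or the missing scoring rule.

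**Conclusion.** The scoring rule is wrong as written and should be fixed. That item 17 earns a point follows from the plan's own maximum of 21 and needs no assumption. The shift of 1 to 5 points per switching woman assumes that skipped items add nothing and that items 1–16 do not change. Of that shift, 1 point is artefact and 0 to 4 points are a mixture. Women with the same status at both visits contribute no artefact to the raw change, so its distortion comes only from those who switch. How many do, and in which arm, cannot be known from the documents. The effect on the treatment estimate is therefore of unknown size and direction, and nothing here shows that the trial's result will be biased. In a pilot without a focus on testing this is a moderate point, but it concerns the definition of the primary endpoint and is cheap to settle in advance.

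**What to change.** In Section 10.4.1, before data are seen:
1. Exclude item 17 from the sum and correct the range to 0–20.
2. State that skipped items 18–21 add 0, so that every woman who completes the form has a total. Acknowledge that a skip effect of up to 4 points remains.
3. Pre-specify the sum of items 1–16 (0–16, asked of every woman) as a supporting analysis of the primary change. It does not move mechanically with activity status.
4. Tabulate the item 17 answer by arm and visit.

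The cost is a protocol amendment with IRB approval (Section 13.2), one extra analysis and one table; no new data are needed. The sexual-impact items stay in the primary score. The drawback is that the reliability cited in Sections 2.1 and 4.2.1 is for the 21-question form, so the documents offer no such support for the 20-item sum or for items 1–16. That is a reason to keep the latter as supporting. A separate analysis of women active at both visits is not requested, because Section 10.4.6 plans no sub-group analysis.
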